8.3.9.2 Discontinuation from Study Participation

When a participant (or caregiver as applicable) requests to discontinue study participation, the participant will undergo an ET Visit as described in Table 2 in Section 1.

The only exception to this requirement is when consent is withdrawn for all study procedures or the participant loses the ability to consent freely (e.g., is imprisoned or involuntarily incarcerated for the treatment of either a psychiatric or physical illness).

Expectations are as follows:

- Participants should notify the investigator of the decision to withdraw consent from future follow-up **in writing**, whenever possible
- The withdrawal of consent should be explained in detail in the medical records by the investigator, as to whether the withdrawal is from further treatment with study medication only (see Section 8.3.9.1), or also from study procedures and/or Week 52/PTFU (see Section 1), and entered on the appropriate eCRF page
- In the event that vital status (whether the participant is alive or dead) is being measured, publicly available information should be used to determine vital status only as appropriately directed in accordance with local law
- If the participant withdraws consent for disclosure of future information, the sponsor may retain and continue to use any data collected before such a withdrawal of consent

The following procedures must be followed upon participant withdrawal:

- Assessments for the ET Visit must be performed, provided that the participant has not withdrawn consent for these activities
- All required eCRF pages must be completed, including the date of and explanation for the withdrawal
- As indicated, appropriate follow-up and/or alternate medical care must be arranged for the participant outside of sponsor responsibility
- Participants who discontinue from study participation (yet have not withdrawn consent) may decline further study visits, however, they will be offered additional visits for the purpose of BMD assessment (see Section 8.5.3.8) and immunogenicity testing (see Section 8.5.3.6).

8.3.9.3 Lost to Follow-Up

- All reasonable efforts must be made to locate participants to determine and report their ongoing status. This includes follow-up with persons authorized by the participant
- Lost to follow-up is defined as the inability to reach the participant after a minimum of 3 documented phone calls, faxes, or emails as well as lack of response by participant to one registered mail letter. All attempts should be documented in the participant's medical records
- If it is determined that the participant has died, the site will use permissible local methods to obtain date and cause of death
- If investigator's use of third-party representative to assist in the follow-up portion of the study has been included in the participant's informed consent, then the investigator may use a sponsor-retained third-party representative to assist site staff with obtaining participant's contact information or other public vital status data necessary to complete the follow-up portion of the study
- The site staff and representative will consult publicly available sources, such as public health registries and databases to obtain updated contact information

- If, after all attempts, the participant remains lost to follow-up, then the last known alive date as determined by the investigator should be reported and documented in the participant's medical records

8.3.9.4 Replacement of Participants

Participants who discontinue from study medication or from study after randomization will not be replaced. Participants who discontinue participation in the study after randomization will not be allowed to reenroll.

8.4 Treatment

Study medication is defined as any investigational treatment(s), marketed product(s), placebo or medical device intended to be administered to a study participant according to the study randomization or treatment allocation.

Each study medication must be listed as either an IP or non-IP.

Study treatment includes both IP and non-IP and can consist of the following:

- All products, active or placebo, being tested or used as a comparator in a clinical study.
- Study required premedication
- Other drugs administered as part of the study that are critical to claims of efficacy (e.g., background therapy, rescue medications)
- If specific criteria are required for treatment in a given phase of the study (e.g., extension phase), provide detailed criteria in this Section
- Diagnostic agents: (such as glucose for glucose challenge) given as part of the protocol requirements must also be included in the dosing data collection.

An IP, also known as investigational medicinal product in some regions, is defined as a pharmaceutical form of an active substance or placebo being tested or used as a reference in a clinical study, including products already with a marketing authorization but used or assembled (formulated or packaged) differently than the authorized form, or used for an unauthorized indication, or when used to gain further information about the authorized form.

Study medication includes both BMS-986036 and placebo and is described in [Table 5](#) below.

Other medications used as support or escape medication for preventative, diagnostic, or therapeutic reasons, as components of the standard of care for a given diagnosis, may be considered as non-IPs.

Table 5 Study Medications

Product	Potency	IP/Non-IP	Blinded or Open Label	Packaging/Appearance	Storage Conditions (per Label)
BMS-986036	10 mg/mL	IP	Blinded	Pre-Filled Syringe	Refer to the label on the container
BMS-986036	20 mg/mL	IP	Blinded	Pre-Filled Syringe	Refer to the label on the container
Placebo	0 mg/mL	IP	Blinded	Pre-Filled syringe	Refer to the label on the container

IP = investigational product; non-IP = non-investigational product

8.4.1 Treatments Administered

The investigator must ensure that the IP will be used only in accordance with the protocol. The study medication doses, dosing frequency and route of administration for each participant are shown in Table 6 below.

Table 6 Study Medication Doses, Dosing Frequency, and Route of Administration

Study Treatment	Unit Dose Strength(s)/Dosage Level(s)	Frequency of Administration	Route of Administration
BMS-986036 10 mg arm	1 mL/10 mg/mL BMS- 986036	Once weekly	Subcutaneous
	1 mL placebo		
BMS-986036 20 mg arm	1 mL/20 mg/mL BMS- 986036	Once weekly	Subcutaneous
	1 mL placebo		
BMS-986036 40 mg arm	2 × 1 mL/20 mg/mL BMS- 986036	Once weekly	Subcutaneous
Placebo	2 × 1 mL placebo	Once weekly	Subcutaneous

8.4.2 Study Medication Administration

Participants should be instructed to make every effort to administer study medication on the same day each week at approximately the same time of day. Each weekly administration will consist of 2 SC injections.

On Day 1 and at the Week 4, 8, 12, 16, 20, 24, 32, and 40 Visits, study medication will be self-administered by the participant or administered by their designee at the study site as part of the participant's scheduled study visits. At those visits, study medication dosing should be held until all study-related assessments, including participant questionnaires, vital signs, ECG, AE evaluation, physical examinations, and laboratory sample collection (including trough [predose] PK) have been completed.

If a study visit occurs on a day that is not a planned dosing day, the participant should continue to administer the medication on the planned dosing day; all study-related assessments will continue to be performed at the planned study visit (in-clinic administration of study drug would not occur).

Study medication is blinded and is supplied in a pre-filled syringe. Each participant will be dispensed a treatment kit containing 2 smaller boxes (for each weekly administration). Each smaller box will contain 1 prefilled syringe of the medication. Both syringes will be administered in the abdominal area at different locations per training guidelines. Study medication will be assigned by the IRT system.

Guidance and training on administration should be given to the participant (or caregiver, if applicable) prior to the first administration. At a minimum, the first administration should be done by the participant under the supervision of qualified site personnel. Training may be repeated as necessary at any study visit at the discretion of the investigator to maintain treatment compliance. When injections are administered at the site during study visits, site staff may observe the injection to ensure proper technique is being employed. Participants will be required to capture the date, time, and location of each injection on the supplied study medication administration card.

Specific instructions for study medication administration as well as training materials for participants (or caregivers, if applicable) are in the Pharmacy Manual.

8.4.3 Method of Treatment Assignment

After receiving the signed ICF but before any other study-related procedures are performed, the investigative site will access the enrollment option of the IRT system for assignment of a participant number (including participants not subsequently randomized or treated). This number is assigned sequentially by the system and will be unique across all sites. If a potential participant is rescreened, a new identification number will be used.

Randomization will be conducted in the following manner:

- Eligible participants will be randomized by the IRT using a prespecified schedule in a double-blind manner to 10 mg BMS-986036, 20 mg BMS-986036, 40 mg BMS-986036, or placebo arms in a 1:1:1:1 ratio based on the stratification factors specified in Section 8.1
- The IRT will provide study medication kit numbers that contain the appropriate study medication (BMS-986036 or placebo) for dispensation to that participant

At subsequent study visits as listed in the Schedule of Activities (Section 1), the investigator or designee will access the IRT to receive the corresponding kit numbers assigned to the participant for the purpose of dispensing study medication.

8.4.4 Blinding of Study Medication

8.4.4.1 Maintaining the Blind

Blinded treatment assignments will be managed using the IRT. All syringes and syringe contents (BMS-986036 10 mg/mL, BMS-986036 20 mg/mL, and placebo) are identical in appearance. Investigative site staff, sponsor and designee personnel, and participants and their families will remain blinded to treatment assignments. Study medication will be administered in a double-dummy manner as described in Section 8.4.2 in order to maintain the blind.

Sponsor and designee personnel may be unblinded once all participants have completed the Week 52/PTFU Visit and all data have been collected through that time point to facilitate analyses. Designated sponsor staff may be unblinded (obtain the randomization codes) prior to database lock to facilitate the bioanalytical analysis of PK samples and immunogenicity. A

bioanalytical scientist in the sponsor Bioanalytical Sciences department (or a designee in the external central bioanalytical laboratory) will be unblinded to (may obtain) the randomized treatment assignments in order to minimize unnecessary bioanalytical analysis of samples.

8.4.4.2 Circumstances for Unblinding

In the event of a medical emergency or pregnancy in an individual participant where knowledge of the study medication is critical to the participant's medical management, the blind for that participant may be broken by the investigator. The participant's safety takes priority over any other considerations in determining if a treatment assignment should be unblinded.

Before breaking the blind of an individual participant's treatment, the investigator should determine that the unblinded information is necessary (i.e., that it will alter the participant's immediate management). In many cases, particularly when the emergency is clearly not related to the IP, the problem may be properly managed by assuming that the participant is receiving active product. It is highly desirable that the decision to unblind treatment assignment be discussed with the medical monitor, but the investigator always has ultimate authority for the decision to unblind. The actual TASK of unblinding can be delegated by the investigator to a designee assigned the task on the Delegation of Authority. The principal investigator or appointed designee should only call in for emergency unblinding AFTER the decision to unblind the participant has been documented.

For this study, the method of unblinding for emergency purposes is through the IRT system. In case of an emergency, the investigator has unrestricted access to randomization information via IRT and is capable of breaking the blind through the IRT system without prior approval from the sponsor. After the unblinding, the investigator shall notify the medical monitor and/or study director. The method of unblinding for emergency purposes is described in the IRT Manual. Participant and unblinded treatment information and the reason for the blind being broken must be recorded on the appropriate study status page of the eCRF.

In cases of accidental unblinding, the site should contact the medical monitor and ensure every attempt is made to preserve the blind. Any request to unblind a participant for nonemergency purposes should be discussed with the medical monitor.

8.4.5 Study Medication Preparation, Handling, Storage, and Accountability

The IP should be stored in a secure area according to local regulations. It is the responsibility of the investigator to ensure that IP is dispensed only to study participants. The IP must be dispensed only from official study sites by authorized personnel according to local regulations.

The product should be stored in a refrigerator (2°C through 8°C [35.6°F through 46.4°F]) and protected from light. If concerns regarding the quality or appearance of the study medication arise, the study medication should not be dispensed, and the sponsor should be contacted immediately.

IP documentation must be maintained. This includes documentation of all processes required to ensure drug is accurately administered, drug storage, administration, and, as applicable, storage temperatures, and use of required processes.

Further details on accountability of study medication are in the Pharmacy Manual.

Further guidance and information on final disposition of unused and returned study medication and study supplies is provided in [Appendix 1](#).

8.4.6 Dose Modification

8.4.6.1 Modification of Dose

No dose reductions or modifications are allowed. If a participant interrupts treatment due to an AE, study medication may be restarted after consultation with the medical monitor.

8.4.6.2 Dose Interruption

If a participant has abnormal laboratory test result(s) and/or clinical AE(s) that, in the judgment of the investigator, could place the participant at risk, study medication administration should be interrupted, and the investigator should notify the medical monitor. Participants may receive further study medication when the AE or abnormal laboratory finding is resolved.

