8.3.9 Withdrawal of Participants

8.3.9.1 Discontinuation of Study Medication

Participants MUST discontinue investigational product (IP) (and non-investigational product [non-IP] at the discretion of the investigator) for any of the following reasons.

- Participant's request to stop study medication. Participants who request to discontinue study medication will be expected to complete an ET (Week 48/ET) Visit and subsequent follow-up visits/procedures per the Schedule of Activities (e.g., Week 52/PTFU; Section 1). The only exception to this is when a participant specifically withdraws consent for any further contact with him/her or persons previously authorized by participant to provide this information. Participants' withdrawal of consent should be explained in detail in the medical records by the investigator as to whether the withdrawal is from further treatment with study medication only or also from study procedures and/or Week 48/ET, Week 52/PTFU Visit, etc. (see Section [8.3.9.2](#))
- Any clinical AE, laboratory abnormality or intercurrent illness, which, in the opinion of the investigator, indicates that continued participation in the study is not in the best interest of the participant
- The participant experiences a major bone fracture or is diagnosed with osteoporosis that requires treatment
- Abnormal liver tests as defined in Section [8.5.3.1](#)
- On 2 consecutive visits (at least 2 weeks apart), a participant has an eGFR < 30 mL/min/1.73 m², according to the *Modification of Diet in Renal Disease Study* equation
- If there is a significant protocol violation. The violation should be discussed with the medical monitor prior to discontinuing study medication
- Loss of ability to freely provide consent through imprisonment or involuntary incarceration for treatment of either a psychiatric or physical (e.g., infectious disease)

illness (Note: Under specific circumstances, a participant who has been imprisoned may be permitted to continue as a participant. Strict conditions apply, and sponsor approval is required)

- The participant becomes pregnant (study medication must be discontinued immediately)

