In the case of pregnancy (see Section 8.5.3.1), the investigator must immediately notify the medical monitor or designee of this event. In the event a participant becomes pregnant during a clinical study, the study medication must be discontinued immediately. In most cases, the study medication will be permanently discontinued in an appropriate manner. The medical monitor should be contacted within 24 hours of awareness of the pregnancy
- Termination of the study or program by the sponsor
- If a participant loses more than 10% of their total body weight, the investigator should contact the medical monitor. The investigator, together with the medical monitor, will then determine whether the participant should continue to take study medication

If study medication is discontinued prior to the participant's completion of the study, the reason for the discontinuation must be documented in the participant's medical records and entered on the appropriate eCRF page. The discontinuation should also be reported via the IRT. As indicated, appropriate follow-up and/or alternate medical care must be arranged for the participant. Please notify the medical monitor as soon as possible when discontinuation of study medication is being considered.

See Section 8.4.6 for details regarding dose modification and/or treatment interruption.

Participants who prematurely discontinue study medication will be expected to complete an ET Visit and subsequent follow-up visits/procedures per the Schedule of Activities, including a Week 52/PTFU Visit (Table 2 in Section 1), DXA and Immunogenicity Follow-Up Visit(s) (Table 3 in Section 1) (see Section 8.5.3.6). The only exception to this requirement is when consent is withdrawn for all study procedures or the participant loses the ability to consent freely (i.e., is imprisoned or involuntarily incarcerated for the treatment of either a psychiatric or physical illness). Participants who discontinue study medication will not be replaced (see Section 8.3.9.4).

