- Participants with elevated Baseline aminotransferase values experience additional increases greater than $2\times$ the Baseline (with concomitant elevations of total bilirubin $> 2\times$ ULN) AND ALT and/or AST is > 200 U/L.

If the new elevations in aminotransferases persist and the participant is symptomatic, then the drug should be discontinued, and the participant should be evaluated for other causes of liver injury or disease. The medical monitor should be contacted within 48-72 hours.

If the participant is asymptomatic, the participant should be placed under “close observation”, defined as physical examination and laboratory evaluation 2-3 times per week.

If close observation is not possible, study medication should be discontinued. The frequency of retesting can decrease to once a week or less if abnormalities stabilize or the study medication has been discontinued and the participant is asymptomatic.

Discontinuation or Temporary Interruption of Study Medication

In addition to the reasons for discontinuation described above, study medication should be discontinued or temporarily interrupted if either of the 2 following scenarios occur:

- 1) Aminotransferases (ALT and/or AST) $> 2 \times$ Baseline and aminotransferases $> 3 \times$ ULN and either:
 - i. the increase is accompanied by a concomitant increase in total bilirubin to $> 2 \times$ Baseline OR the INR concomitantly increases by > 0.2 ;

OR

 - ii. there are concomitant signs and symptoms of new-onset fatigue, nausea, vomiting, right upper quadrant pain or tenderness, fever, rash, and/or eosinophilia ($> 5\%$).
- 2) Total bilirubin increases to $> 2 \times$ ULN AND:
 - i. there are concomitant signs and symptoms of new-onset fatigue, nausea, vomiting, right upper quadrant pain or tenderness, fever, rash, and/or eosinophilia ($> 5\%$)

If the above rule is met, a potential DILI work up for competing etiologies (e.g., alcohol use, viral hepatitis, biliary obstruction, autoimmune liver disease) must be performed, and a complete liver profile including INR must be repeated within 48-72 hours. **The medical monitor should be contacted within 48-72 hours.** Study medication can be restarted only if an alternative etiology is definitively identified and liver tests (aminotransferases, total bilirubin and/or INR) have returned to Baseline.

Other Safety Considerations

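### Protocol 8.3.9.1 makes discontinuation mandatory for liver-test events defined in 8.5.3.1, but 8.5.3.1 itself allows interruption and conditional restart

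*Protocol*

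**What the plan says.** Four places in the Protocol bear on what happens to dosing after a liver-test abnormality.

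- **8.3.9.1 (Discontinuation of Study Medication)** opens its list with "Participants MUST discontinue investigational product (IP) (and non-investigational product [non-IP] at the discretion of the investigator) for any of the following reasons". One bullet reads "Abnormal liver tests as defined in Section" 8.5.3.1. The section gives no restart route for that bullet. After the list it adds a general pointer: "See Section 8.4.6 for details regarding dose modification and/or treatment interruption".
- **8.5.3.1 (Adverse Events)**, under its own subheading on discontinuation or temporary interruption, says "study medication should be discontinued or temporarily interrupted if either of the 2 following scenarios occur". It then sets a two-part restart condition: "Study medication can be restarted only if an alternative etiology is definitively identified and liver tests (aminotransferases, total bilirubin and/or INR) have returned to Baseline". Earlier in the same section are other liver criteria. Two of them lead to discontinuation with no interruption option: persistent aminotransferase elevation with symptoms, and an asymptomatic elevation where close observation is not possible.
- **8.4.6.1 (Modification of Dose)** says that after an interruption for an adverse event "study medication may be restarted after consultation with the medical monitor".
- **8.4.6.2 (Dose Interruption)** covers any abnormal laboratory result or adverse event that the investigator judges a risk. It requires interruption and notification of the medical monitor, and then says "Participants may receive further study medication when the AE or abnormal laboratory finding is resolved".

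Neither 8.4.6 passage excepts liver tests or refers to 8.5.3.1, and no section is given precedence.

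**The concern.** The 8.3.9.1 bullet takes its definition from 8.5.3.1 but attaches an outcome that 8.5.3.1 does not impose for its two scenarios. A site that reads 8.3.9.1 ends treatment. A site that reads 8.5.3.1 may interrupt and, if both conditions are met, resume. These are contradictory stopping instructions in participants with cirrhosis.

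The cross-reference is also imprecise. Because 8.5.3.1 holds several liver criteria with different consequences, the bullet could mean all of them, only the two scenarios, or only the discontinuation-only criteria.

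The choice also sets the path to the primary endpoint. Under Protocol 8.1 and 8.5.1.1, early discontinuation brings an Early Termination (ET) Visit, with a biopsy then if at least Week 20 has been completed; before Week 20 the biopsy is only to be considered. An interrupted participant who resumes goes on to the Week 48 biopsy. Under Protocol 9.5.2.1 and SAP 6.1.1, a participant with neither a Week 48 nor an ET biopsy result is a non-responder.

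**Working it through.** The documents give no figure to reproduce; this is a check of text against text. I took an event and applied each section as written.

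| Event | 8.3.9.1 (if the bullet covers it) | 8.5.3.1 | 8.4.6.2 read alone |
|---|---|---|---|
| A. Meets an 8.5.3.1 scenario; tests return to Baseline; another cause definitively found | Discontinue | Interruption and restart permitted | Restart permitted |
| B. Meets an 8.5.3.1 scenario; tests return to Baseline; no other cause found | Discontinue | Restart not permitted | Restart permitted |
| C. Elevation persists with symptoms | Discontinue | Discontinue | No restart while unresolved |

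Reading across the rows:

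1. Row A separates 8.3.9.1 from 8.5.3.1. This is the main conflict, and it does not depend on 8.4.6.
2. Row B separates 8.4.6.2 from the other two, which agree that the participant is not re-dosed. This is the secondary gap.
3. Row C shows no conflict. If the 8.3.9.1 bullet was meant only for the discontinuation-only criteria, the two sections agree, but the bullet does not say so.

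Two readings underlie the table. First, discontinuation in 8.3.9.1 is taken to end treatment: the section attaches an ET Visit and follow-up to it and deals with interruption separately by pointing to 8.4.6. Second, a return to Baseline is taken to count as resolved under 8.4.6.2, which does not define the word. For liver injury, 8.5.3.1 sets Baseline as the mean of the Screening and Day 1 results, and 8.3.2 excludes only ALT or AST above 5 × ULN. A participant can therefore be back at an elevated Baseline without being normal, so the two terms need not coincide.

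Size for the primary endpoint, per event:

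- Timing: a required ET biopsy can fall just after Week 20 instead of at Week 48, so the largest difference is 48 − 20 = 28 weeks.
- Response rate: with about 38 participants per arm (Protocol 6.2), one participant whose response status changes moves that arm's rate by 1/38 = 0.026, or about 2.6 percentage points.

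The number of such events is not given and cannot be derived, so no total effect follows from these figures.

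**The case against.** The strongest reply is that a careful site would not be misled. The liver bullet in 8.3.9.1 points to 8.5.3.1, where the restart limit stands under its own subheading; the pointer to 8.4.6 is a general one after the whole list. The 8.4.6.2 rule is general and permissive, the 8.5.3.1 rule is specific and restrictive, and a site that follows the specific rule complies with both. The medical monitor is also involved throughout: 8.4.6.2 requires notification, 8.4.6.1 requires consultation before restart after an adverse-event interruption, 8.5.3.1 requires contact within 48-72 hours, and 8.5.3 requires urgent safety concerns to be discussed with the sponsor immediately. In addition, the mandatory list is not uniformly absolute: its weight-loss item leaves continuation to the investigator and medical monitor.

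Most of this stands against the 8.4.6 limb, which is why that limb is secondary. It remains a missing cross-reference, because the Protocol does not state that the specific rule prevails. The reply does not reach row A: there the two liver-specific texts themselves disagree, and the medical monitor would be working from the same text.

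Two stronger readings are tempting. A reader might infer that three sections give three different outcomes for one event; no row of the table does so, and each of rows A and B yields only two. A reader might also infer that the Protocol as a whole permits re-dosing after an unexplained liver event. That follows only from 8.4.6.2 read in isolation, without the specific rule and the medical-monitor steps.

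**Conclusion.** The point holds, with medium confidence. If the 8.3.9.1 bullet covers the two 8.5.3.1 scenarios, the sections contradict each other for an event with another cause found and tests back at Baseline. If it does not, the bullet fails to say which criteria it covers. Either way the text needs correcting. The 8.4.6.1 and 8.4.6.2 wording is a lesser gap of the same kind.

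The effect on the primary endpoint is possible but hypothetical. The 28 weeks is a maximum for a required ET biopsy, and the 2.6 points applies only if a participant's response status actually changes. Neither is a predicted bias, and ET biopsies already count in the primary analysis. Because 8.5.3.1 itself leaves a choice between stopping and interrupting, some difference in biopsy timing for similar events could remain after the wording is reconciled.

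**What to change.** Reconcile 8.3.9.1, 8.4.6.1, 8.4.6.2 and 8.5.3.1 so that one named section governs dosing after liver-test events. Specifically:

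- In 8.3.9.1, state which liver criteria of 8.5.3.1 the bullet covers, and align its outcome with that section on whether the event ends treatment or may lead to interruption.
- In 8.4.6.1 and 8.4.6.2, add a sentence saying that liver-test events are handled only under the governing section.

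Which rule applies is a decision for the sponsor's safety physicians; this review does not propose one. The cost is wording in an amendment or clarification letter, with no new procedures.
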